## 10.0 EVALUATION DURING TREATMENT/INTERVENTION

All evaluations/tests and research collections may be performed up to 3 days prior to the patient being treated.

Cycle/Week of Therapy (1 cycle= 6 weeks)	Pre-Study a	Cycle 1 Week 1 i	Cycle 1 Week 3	Cycle 1 Week 5	Cycle 2+ f Week 1	Cycle 2+ f Week 3	Cycle 2+ f Week 5	Off Study g
Weeks on study	-	1	3	5	7	9	11	-
Nivolumab b		X	X	X	X	X	X	
Ipilimumab b		X			X			
Informed consent	X							
Concurrent meds	X	X d	X	X	X			X
Physical exam	X	X d	X	X	X			X
Vital signs (pulse, blood pressure)	X	X d	X	X	X			X
Weight	X	X d	X	X	X			X
Adverse event evaluation	X	X d	X	X	X			X
CBC w/diff, plts	X	X e	X	X	X	X	X	X
Comprehensive panel c	X	X e	X	X	X	X	X	X
TSH	X				X			X
Beta-HCG (serum or urine)	X i							
Request for archival tumor tissue	X							
Research blood draw	X							
Research tumor biopsies k	X k		X k					
Research peripheral blood collection j		X			X			X
Tumor measurements h	X	CT and/or MRI will be performed every 12 weeks (+/- 1 week) (or approximately every 2 cycles). Objective responses should be confirmed with a second assessment performed at least 4 weeks later.						

a: See Section 8.0 for the timing of these tests/evaluations prior to the start of therapy.

b: Study drugs will be administered at the following doses/schedules: nivolumab 3 mg/kg IV every 2 weeks and ipilimumab 1 mg/kg IV every 6 weeks. At the investigator's discretion patients can be treated with nivolumab alone after 4 cycles for safety concerns.

c: Albumin, alkaline phosphatase, total bilirubin, bicarbonate, BUN, calcium, chloride, creatinine, glucose, potassium, total protein, SGOT [AST], SGPT [ALT], sodium.

d: These Week 1 evaluations maybe performed within 3 days prior to the start of treatment.

e: These Week 1 laboratory tests may be done up to 7 days prior to starting treatment. It is unnecessary to repeat these laboratory tests if the screening assessments of the same tests were performed within 7 days prior to the first dose of therapy.

f: These columns reflect the schedule of assessments/treatment required for Cycle 2 and subsequent cycles in the weeks designated.

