g: Off-study evaluation will be performed within 30 days of the patient's last dose of study drug (Exception: Patients for whom removal from the study followed a prolonged interval during which administration of study drugs was held for greater than 30 days, the off-study evaluation needs to be performed within 30 days of the patient's last physical assessment by investigator physician).

h: The treating physician may reschedule radiologyscans due to treatment delays at his or her discretion . If the patient has CT and/or MRI scans completed early for any reason (e.g. suspicion of disease progression), the next set of scans maybe ordered in 12 weeks (+/- 1 week) from that assessment. Please see Section 13.0 regarding the altered schedule of radiographic assessments required for patients being treated beyond initial evidence of tumor progression.

i. Serum or urine pregnancy test is required within 14 days of drug treatment for all women of child-bearing potential.

j: Peripheral blood samples will be collected in 4 CPT tubes (BD, 8-ml capacity, total blood volume collected~32 ml for PBMC purification for flow cytometric analysis) and 1 PAXgene tube (BD order #762165 or equivalent) (for purification of RNA/DNA for TCR analysis). The Cycle 1, Week 1 sample should be obtained prior to drug administration, but not beyond 3 days prior to the start of treatment. Subsequent samples will be obtained on Cycle 2/Week 1, Cycle 3/Week1, and then Off Study. If the collection of all 4 CPT tubes and 1 PAXgene tube are not feasible, this will not be considered a protocol deviation.

k. The first of two research biopsies will be performed anytime prior to Week 1 Day 1. Tumor tissue obtained prior to study consent or treatment as part of standard of care can also be submitted in lieu of performance of the first pre-treatment biopsy, if the Principal Investigator deems it to be of sufficient quantity/quality/timeliness. The second research biopsy will be performed prior to the administration of the second dose of ipilimumab. Exceptions regarding the timing of the second biopsy can be made at the Principal Investigator's discretion, and will not be considered a violation. Patients may be exempt from biopsy if 1) the

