Due to the limited sample size, the analyses investigating the association between correlative markers and BOR will be exploratory. These exploratory analyses will be evaluated within each cohort separately. Categorical markers will be correlated with BOR by Fisher's exact tests. Continuous markers will be correlated with BOR by logistic regression. Immune activation that occurs concomitant with experimental therapy will be serially assessed in the PBMC analysis performed for each patient. Specifically, the changes in T cell subsets that occur with therapy will be analyzed and interpreted as potential indicators of immune activation induced by drug therapy. Proportions of T cell subsets will be calculated with 95% confidence intervals at each time point and plotted over time to reveal any trend. The baseline proportions of T cell subset and changes in these proportions from baseline to last time point will be correlated with the response status univariately.

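### Section 14 reads T cell changes from separate 95% intervals at each visit and names no within-patient estimate, so change is described imprecisely and the plotted mean can drift as the sampled patients thin out

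*Combined protocol and SAP*

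**What the plan says.** The last paragraph of Section 14.0 (Biostatistics) sets out the peripheral blood analysis. It states the aim in terms of change: "the changes in T cell subsets that occur with therapy will be analyzed and interpreted as potential indicators of immune activation induced by drug therapy". The method that follows is "Proportions of T cell subsets will be calculated with 95% confidence intervals at each time point and plotted over time to reveal any trend". A within-patient quantity appears only in the next sentence and for another purpose, association with response: "changes in these proportions from baseline to last time point will be correlated with the response status univariately". The paragraph opens by limiting its own weight: "Due to the limited sample size, the analyses investigating the association between correlative markers and BOR will be exploratory".

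The sampling times are in Section 10.0. After a Cycle 1 Week 1 baseline, footnote j says "Subsequent samples will be obtained on Cycle 2/Week 1, Cycle 3/Week1, and then Off Study". The table header note adds "All evaluations/tests and research collections may be performed up to 3 days prior to the patient being treated". For imaging, the same table says "CT and/or MRI will be performed every 12 weeks (+/- 1 week) (or approximately every 2 cycles". Section 13.0 lists progression as a reason for removal from study, and then allows treatment beyond progression on the investigator's assessment.

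No paired contrast, longitudinal model, common patient set or rule for missing samples is given for the activation question.

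**The concern.** The question is whether a patient's T cell subsets change on treatment. The named summary describes the patients sampled at each visit and leaves the reader to infer change by eye. Two things follow.

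- **Precision.** An interval at one visit carries the full spread between patients. Comparing two such intervals ignores that a patient's own baseline predicts the later value, although the protocol draws serial samples from each patient.
- **Composition.** Nothing requires the same patients to contribute at each point. If those who stop being sampled differed at baseline, the mean shifts through selection alone. Off Study samples come from patients who have left, at varying times, so that point is not a further step on a common time axis.

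At stake is the reading of an exploratory endpoint: a real shift may look like noise, or a change in who is sampled may be read as a drug effect.

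**Working it through.** **Sample size.** The plan states no figure for the T cell analysis. The maximum per cohort comes from the two-stage design in Section 14.0: 18 + 14 = 32. An exact binomial calculation of that design (at least 1 response in 18, then at least 4 in 32) gives type I error 0.072 at a 5% response rate and power 0.901 at 20%, consistent with the stated 10% and 90%. So n = 32 is the upper limit.

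**Precision, nobody missing.** Work in units of the between-patient SD, taken as equal at both visits. The documents give no within-patient correlation ρ, so a range is assumed.

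- Treated as independent: half-width = t(62) × √(1/32 + 1/32) = 1.999 × 0.250 = 0.50 SD.
- Paired: half-width = t(31) × √(2(1 − ρ)/32), with t(31) = 2.040.
  - ρ = 0.5: 2.040 × 0.177 = 0.36 SD
  - ρ = 0.7: 2.040 × 0.137 = 0.28 SD
  - ρ = 0.9: 2.040 × 0.079 = 0.16 SD

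Ignoring the pairing widens the interval for change by a factor of about 1.4, 1.8 and 3.1 respectively. This part needs no assumption about dropout.

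**Precision with smaller numbers.** Same formulas, with n patients at baseline and m with both samples:

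| n, m | Independent | Paired, ρ = 0.5 | Paired, ρ = 0.7 | Paired, ρ = 0.9 |
|---|---|---|---|---|
| 32, 32 | 0.50 | 0.36 | 0.28 | 0.16 |
| 32, 22 | 0.56 | 0.44 | 0.34 | 0.20 |
| 32, 16 | 0.62 | 0.53 | 0.41 | 0.24 |
| 18, 18 | 0.68 | 0.50 | 0.39 | 0.22 |

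The gain depends on ρ. At ρ = 0.3 with half the patients missing (32, 16), pairing gives 0.63 SD against 0.62 SD, so it no longer helps precision.

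**Timing.** Two 6-week cycles put Cycle 3 Week 1 on day 85, so its sample falls on days 82 to 85. The first scan is due at 12 weeks ± 1 week, nominally days 78 to 92. The sample therefore lies inside the scan window. A progressor scanned early in the window and removed gives no week-13 sample. One scanned later may already have given it, and one treated beyond progression can give it. Cycle 2 Week 1 (week 7) precedes the first scheduled scan, so baseline to week 7 is largely unaffected.

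**Drift with no true change.** Let q be the fraction lost before week 13, and let S and L be the baseline means of those who stay and those who leave.

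- Baseline mean = qL + (1 − q)S
- Week-13 mean = S
- Drift = q(S − L)

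With an assumed gap of 0.5 SD:

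- q = 0.2: 0.2 × 0.5 = 0.10 SD
- q = 0.3: 0.3 × 0.5 = 0.15 SD
- q = 0.5: 0.5 × 0.5 = 0.25 SD

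A simulation with n = 32 and 4,000 runs per setting agreed: drift of about 0.15 SD at 30% loss and 0.25 SD at 50%, with the mean paired change in the same runs within 0.01 SD of zero. The separate intervals failed to overlap in under 1% of these runs, so the drift would show as a slope in the plotted means and rarely as separated intervals.

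**The case against.** Section 14 does say that PBMCs are assessed serially for each patient and that changes will be analysed, and it does specify one within-patient change. A fair reader could take the plot as description alongside that. The first statement names no estimator, however, and the specified change is used only against response. The gap is therefore narrow: no within-patient estimate is named for activation itself.

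The plan also sets no test, overlap rule or threshold for the plot. That stands. A reader might infer that the plan's method has a calculable low power to detect a change. The documents do not support this, because power would belong to an unpaired test that the plan never proposes. The half-widths above describe precision only.

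A reader might also infer that first-scan progressors normally leave before week 13, so that the visits compare different patients. The documents do not support that either. The scan window straddles the sample, footnote h to the Section 10.0 table lets scans be rescheduled for treatment delays, and treatment beyond progression is allowed. No progression rate is given. Any week-13 group is a subset of the baseline patients.

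Pairing is also not a full remedy. If leavers would have changed differently from stayers, the paired week-13 change in patients with both samples is itself selected.

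Finally, the work is exploratory and the data remain linked by patient, so a paired analysis stays possible without an amendment. This limits the weight of the point but does not justify leaving the method unnamed.

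**Conclusion.** The point holds in a limited form. For its activation question the plan names a cross-sectional summary where a within-patient one fits better. Under the stated correlations, with complete samples at n = 32, the cost in precision is a half-width of about 0.50 SD against 0.36 to 0.16 SD.

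The composition effect at week 13 is possible but of unknown size. The 0.10 to 0.25 SD range rests wholly on an assumed loss and an assumed baseline gap. The documents support saying that some first-scan progressors can leave before that sample, and no more than that.

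Response, PFS, safety and the go/no-go rule are unaffected. This is an inexpensive improvement to an exploratory analysis, worth making before the samples are analysed.

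**What to change.** In Section 14.0, replace the sentence on per-visit intervals with wording to this effect: For each subset and within each cohort, the within-patient change from Cycle 1 Week 1 to Cycle 2 Week 1 and to Cycle 3 Week 1 will be estimated with a paired 95% confidence interval in patients with both samples, or from a mixed model with patient as a random effect using all samples from these visits. The number of patients contributing will be reported at each visit. Per-visit means and intervals will be plotted for description only. Off Study samples will be shown separately and not as a point on the trend.

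Add one sentence noting that the paired week-13 change applies to patients with both samples and may still be selected if those who left would have changed differently.

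The cost is a wording change in one section. Samples, assays, visits and clinical procedures stay the same.

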### 4.2 Intervention

Enrolled patients will be treated with nivolumab 3 mg/kg every 2 weeks plus ipilimumab 1 mg/kg every 6 weeks (1 cycle= 6 weeks). Radiographic imaging and clinical assessments for RECIST v1.1 response assessment will be performed at baseline and then approximately every 12 weeks (+/- 1 week)(or approximately every 2 cycles). Given the potential for delayed responses following short periods of disease progression, subjects may continue to receive therapy beyond radiographic progression in the absence of clinical deterioration and after discussion with the Principal Investigator. Patients will be continued on therapy until disease progression, unacceptable toxicity, patient withdrawal of consent, or investigator's discretion. Adverse events will be monitored from the start of therapy until 30 days after the last dose of drug.

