### **12.1 Definitions**

**Evaluable for toxicity.** All patients will be evaluable for toxicity from the time of their first treatment with nivolumab and ipilimumab.

**Evaluable for objective response.** Only those patients who have measurable disease present at baseline and have received at least one dose of therapy will be considered evaluable for response. These patients will have their response classified according to the definitions stated below. (Note: Patients who exhibit objective disease progression prior to the end of cycle 1 will also be considered evaluable.)

**Evaluable Non-Target Disease Response.** Patients who have lesions present at baseline that are evaluable but do not meet the definitions of measurable disease, have received at least one cycle of therapy, and have had their disease re-evaluated will be considered evaluable for non-target disease. The response assessment is based on the presence, absence, or unequivocal progression of the lesions.

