#### **Treatment Beyond Progression**

Accumulating evidence indicates a minority of subjects treated with immunotherapy may derive clinical benefit despite initial evidence of PD.

Subjects will be permitted to continue treatment beyond initial RECIST 1.1 defined PD as long as they meet the following criteria:

- Investigator-assessment that continued protocol therapy could elicit future clinical benefit and the subject is tolerating study treatment.

The assessment of clinical benefit should take into account whether the subject is clinically deteriorating and unlikely to receive further benefit from continued treatment.

Followup imaging to evaluate for further progression will be performed 4-8 weeks after the initial scan demonstrating disease progression. Subsequent scans may be performed every 8 weeks (+/- 1 week) or every 12 weeks (+/- 1 week) per the investigator's discretion. Subjects should discontinue study therapy upon evidence of further progression, defined as an additional 10% or greater increase in tumor burden volume from time of initial progression (including all target lesions and new measurable lesions).

New lesions are considered measurable at the time of initial progression if the longest diameter is at least 10 mm (except for pathological lymph nodes, which must have a short axis of at least 15 mm) and was not present during baseline scan. Any new lesion considered non-measurable at the time of initial progression may become measurable and therefore included in the tumor burden measurement if the longest diameter increases to at least 10 mm (except for pathological lymph nodes, which must have an increase in short axis to at least 15 mm).

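### The T-cell change to the last sample is correlated with response, but when that sample is taken depends partly on the outcome

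*Combined protocol and SAP*

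**What the plan says.** Section 14.0, in its paragraph on correlative markers, says that "changes in these proportions from baseline to last time point will be correlated with the response status univariately". The last time point is not defined, and no allowance is made for time on treatment. The same paragraph labels the marker analyses exploratory, runs them within each cohort, and names logistic regression for continuous markers. It also plans subset proportions with confidence intervals at each time point, plotted over time, but does not say that the plots are split by response.

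Section 10.0, footnote j, sets the blood schedule after the pre-dose Cycle 1/Week 1 sample: "Subsequent samples will be obtained on Cycle 2/Week 1, Cycle 3/Week1, and then Off Study". Footnote g fixes the final visit relative to dosing: "Off-study evaluation will be performed within 30 days of the patient's last dose of study drug". After a hold of more than 30 days, footnote g ties that visit to the last physical assessment instead. Section 4.2 sets no maximum duration: "Patients will be continued on therapy until disease progression, unacceptable toxicity, patient withdrawal of consent", or until the investigator decides otherwise.

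**The concern.** The explanatory variable is measured at a time that the outcome helps to set. Progression stops dosing, dosing sets the Off Study visit, and under Section 12.4.3 progression also closes the window for best response. Responders and non-responders can therefore differ at the last sample in weeks since baseline, cumulative exposure and disease state, for reasons unrelated to the marker. A univariate test cannot separate these differences from a marker effect. The Off Study sample may also be drawn after best response has been settled, so it is not a clean predictor.

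At stake is the exploratory objective, which is to find biologic correlates of efficacy. A spurious association, or a masked one, could be carried forward as a candidate marker. The comparison of baseline proportions in the same sentence of Section 14.0 is not affected.

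**Working it through.** The plan states no figure for this analysis, so there is none to reproduce. The check has two parts.

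**1. Timing, from the documents**

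- Cycles last 6 weeks, so Cycle 2/Week 1 is study week 7 and Cycle 3/Week 1 is study week 13 (6 and 12 weeks after the start). Off Study has no fixed week.
- Short end: Section 12.1 says "Patients who exhibit objective disease progression prior to the end of cycle 1 will also be considered evaluable". The only later sample for such a patient can be Off Study, before week 7.
- Responders: scans are every 12 weeks (+/- 1), and Section 10.0 adds that "Objective responses should be confirmed with a second assessment performed at least 4 weeks later". On scheduled scans a confirmed response comes no earlier than 11 + 4 = 15 to 12 + 4 = 16 weeks. This dates the confirming scan, not the last blood draw.
- Prolonged stable disease lengthens time on drug in non-responders. So does treatment beyond progression, for which Section 13.0 says "Followup imaging to evaluate for further progression will be performed 4-8 weeks after the initial scan demonstrating disease progression". Both narrow or reverse the gap.
- If the phrase means the last available sample, a responder still on drug contributes Cycle 3/Week 1 while patients who have stopped contribute Off Study. The imbalance can then run the other way.

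**2. Size, under stated assumptions**

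The documents give no durations and no T-cell drift. The model takes 6 responders and 26 non-responders in a cohort of 32 (20% of 32 is 6.4) and no true link between marker and response:

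change = drift × weeks/26 + N(0,1), in SD units

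Assumed last samples, uniform within each range:

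- responders at weeks 30-72 (mean 51), or 12 weeks after the start if still on drug;
- non-responders at weeks 12-24 (mean 18), or 24-72 (mean 48) if stable.

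Bias at drift 1.0 = gap in mean weeks / 26. The test is the logistic likelihood-ratio test, with 20,000 datasets per cell. The plan sets no threshold, so p<0.05 serves only as a yardstick.

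| Scenario | Mean week, responders vs non-responders | Gap (weeks) | Bias at drift 1.0 (SD) | % with p<0.05 at drift 0 / 0.25 / 0.5 / 0.75 / 1.0 |
|---|---|---|---|---|
| A. No overlap | 51 vs 18 | 33 | 1.27 | 6.0 / 12.4 / 29.6 / 54.5 / 76.7 |
| B. 40% of non-responders stable | 51 vs 0.6×18 + 0.4×48 = 30 | 21 | 0.81 | 6.3 / 8.6 / 14.5 / 23.6 / 32.1 |
| C. 60% stable | 51 vs 0.4×18 + 0.6×48 = 36 | 15 | 0.58 | 6.2 / 7.2 / 9.9 / 14.8 / 18.3 |
| D. As B, one third of responders on drug | (2/3)×51 + (1/3)×12 = 38 vs 30 | 8 | 0.31 | 6.1 / 6.7 / 7.8 / 9.4 / 11.0 |
| E. As B, all responders on drug | 12 vs 30 | -18 | -0.69 | 6.5 / 7.6 / 12.1 / 18.3 / 26.3 |
| F. As A, drift levels off at week 24 | effective 24 vs 18 | 6 | 0.23 | 6.4 / 6.4 / 7.1 / 7.9 / 8.9 |

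In E at drift 1.0 every such result points the opposite way. The fixed week-7 change gives 5.8-6.5% in every cell, which is the small-sample level of this test. With the exact Mann-Whitney test at drift 1.0, A to F give 68.3 / 29.3 / 16.1 / 8.9 / 22.3 / 7.2%, and the fixed sample gives 4.5-5.1%.

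A second model used a two-sided t test, SD 5 percentage points, mean Off Study at week 18 for non-responders and week 36 or 52 for responders, and about 4,000 datasets per case. Again there was no true link:

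- steadily rising subset: spurious difference of +2.8 to +3.5 points, 20-29% with p<0.05;
- transient change: -4.4 to -6.0 points, 40-62%;
- no time trend: about 0, 4-5%;
- fixed week-13 sample: about 0, 4.8-5.4% in all cases.

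The sign depends on the subset's time course and on who is still on drug. The documents settle neither.

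**The case against.** The strongest reply is that this matters little. Section 14.0 already calls the analyses exploratory because of sample size, sets no significance threshold for them and attaches no decision. That stands, and it limits the importance of the point.

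The large figures also depend on assumptions outside the documents. The 77% needs non-overlapping durations and linear drift continuing to week 72. Milder cases at drift 1.0 give less:

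- 40% stable with a week-24 plateau: about 7%;
- 40% stable with one third of responders stopping at weeks 12-30, for instance for toxicity: about 14%, against 32%;
- only two responders (5% of 32 is 1.6): about 44% without overlap and 16% with 40% stable, against 77% and 32%.

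Early toxicity stops are plausible: Section 3.0 reports 5 of 39 patients (13%) stopping this regimen for treatment-related events in another tumour type. These cases stand too. They lie within the range shown, and 77% should not be read as an estimate. Progressors in cycle 1 are not in the model; including them could widen the gap.

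Finally, Section 14.0 does not exclude fixed-time correlations, since its logistic regression for continuous markers names no time point. That is true, but the one change-from-baseline comparison it does specify uses the floating sample. Following the plan as written can therefore give a confounded association.

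**Conclusion.** The concern holds. The change to the last time point is undefined. On the schedule it means a sample whose timing depends partly on response, so the planned correlation can be biased in either direction. If the subset has no time trend and is not affected by the reason for stopping, this bias disappears.

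Confidence in the mechanism is high because it follows from the text. The size is not known: under the assumed durations and drifts it runs from no visible inflation to large inflation, including a reversed sign. The effect is confined to one exploratory analysis. The response-rate test, the two-stage rule, PFS and safety are untouched. The change is worth making because it is cheap, not because the trial's main conclusions are at risk.

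**What to change.** In Section 14.0, replace the change to the last time point with the change from baseline to Cycle 2/Week 1 as the response-linked analysis. That sample falls at week 7, before the first scheduled scan. Add the change to Cycle 3/Week 1 as support, in patients still on study then. Report Off Study changes descriptively by response, with weeks since baseline shown. A model of all samples that includes time since baseline is an acceptable alternative. State how many patients lack a week-7 sample, by response status.

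The edit to the plan is short and needs no new visit or blood draw, but it adds a few tabulations. The real cost is lost patients. Anyone without a week-7 sample drops out, and their number cannot be foreseen, since footnote j says "If the collection of all 4 CPT tubes and 1 PAXgene tube are not feasible, this will not be considered a protocol deviation". Patients who progress in cycle 1 would be among those lost, and all of them are non-responders. The result therefore applies only to patients who reach week 7. Week 7 also addresses early change only, which is why the Cycle 3/Week 1 analysis and the descriptive Off Study report should stay.
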